B.1.4 Aim 4 (Secondary): We aim to study the impact of sex, access-site (i.e., radial vs femoral), and concomitant use of glycoprotein (GP) IIb/IIIa inhibitors on the association of ACT target with bleeding. It has been shown that female sex is associated with higher ACT targets during PCI (17), and work from our group has shown an important observed interaction with myocardial infarction risk in women, but not men, with ACT targets >350 seconds(18). This observation of a potential differential sex-specific interaction has not previously been reported and requires validation in a prospective study. In addition, it has previously been shown that women appear to be at higher risk for developing forearm bleeding complications after transradial catheterization. The use of transradial PCI has steadily increased in the United States, though adoption of this technique remains lower than that observed in Canada and Europe. However, recent internal PCI data from the cardiac catheterization laboratory at Mayo Clinic Rochester has shown increasing utilization of the radial artery for PCI, now over 50%. At Mayo Clinic Florida, the percentage of radial access is over 70% and is considered the default access site for catheterization. It remains unknown whether ACT targets can be similarly interpreted for radial PCI, as these original targets were derived from studies in primarily transfemoral access cohorts with larger vascular access sheaths. Finally, the additional use of GP IIb/IIIa inhibitors in UFH-treated patients has been associated with higher rates of major and minor bleeding (9), thus lower ACT target values (i.e., 200-250 sec) are recommended in patients concomitantly treated with these agents. In the Mayo Clinic experience, there was no apparent interaction by GP IIb/IIIa inhibitor status when testing the association of ACT values to outcomes, however, baseline characteristics of groups receiving or not receiving these agents differed and residual confounding may have been present (18). The OPTIMAL-ACT trial will incorporate a pre-specified analysis with specific ACT targets in patients receiving GP IIb/IIIa inhibitors to better understand ACT targets and outcomes.

B.1.5 Aim 5 (Exploratory): We will explore the association of ACT targets with individual components of NACE and stent thrombosis for purposes of hypothesis generation.

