Specific exclusions would include patients receiving low-molecular weight heparin at treatment doses with last dose within 6 hours of coronary angiography (patients on low-molecular weight heparin (LMWH) for venous thromboembolism prophylaxis would be eligible), upstream treatment with GP IIb/IIIa inhibitors within the previous 72 hours, use of warfarin or a novel oral anticoagulant at the time of the procedure, patients being bridged with LMWH in the peri-procedural setting, PCI performed within the proceeding 30 days, need for rotational atherectomy, and planned use of bivalirudin as the procedural anticoagulant. If the operator was uncertain as to whether bivalirudin would be used, the patient would be eligible for screening and randomization. In the event that bivalirudin was selected to support the PCI procedure, the patient would be excluded from the OPTIMAL-ACT trial and recommendations would be for dosing bivalirudin per the manufacturer's instructions with ACT monitoring as used in the REPLACE-2 trial (22), which included ACT value 5 minutes after initial bolus and if <225 sec, an additional bolus of 0.3 mg/kg if needed. The following exclusion criteria for OPTIMAL-ACT are as follows:

[figure not shown]
Exclusion Criteria:

- Receipt of LMWH at treatment dose (not DVT prophylaxis dose) within 6 hours of coronary angiography
- Prior GP IIb/IIIa use within the previous 72 hours
- Use of warfarin (vitamin K antagonist) or direct oral anticoagulant
- Patients on LMWH bridging strategy
- PCI within prior 30 days
- Planned use of bivalirudin as the procedural anticoagulant
- Rotational atherectomy
- Excimer laser coronary angioplasty
- Chronic total occlusions
- Patients with active bleeding disorders or bleeding diathesis
- Patients with ST-segment elevation myocardial infarction
- Patient with clinical evidence of cardiogenic shock (defined as SBP<90 mmHg for ≥30 min OR support to maintain SBP ≥90 mmHg AND evidence of end-organ hypoperfusion (urine output <30 mL/h or cool extremities)
- Chronic kidney disease stage 4/5 (GFR 30 mL/min)

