Patients would be randomized to one of three ACT target groups (Figure 1). Patients will undergo randomization (1:1:1) to either low ACT target, medium ACT target, or high ACT target using a software automatic program (insert information on SDMS). ACT target ranges would be modified based on intended or provisional use of GP IIb/IIIa inhibitors. Target ranges for the OPTIMAL-ACT trial were based on both review of practice guideline recommendations, including the uncertainty expressed in the guidelines regarding ACT values and outcomes (4), and consensus agreement by study interventional cardiologists regarding clinical equipoise in the target ranges studied. PCI would be performed per routine clinical practice and selection of adjunctive oral antiplatelet therapies would be at the discretion of the operator and in accordance with clinical practice guidelines (4). Patients would be observed post PCI for

[figure not shown]
bleeding (primary endpoint), defined as BARC 1, 2,3 or 5 and EASY I-V (Appendix) and for NACE (i.e., ischemic events or bleeding as the primary safety endpoint). Follow-up would extend for 30-days post PCI for occurrence of the primary endpoint and primary safety endpoint. A dedicated telephone script will be used to contact the patient 30 days post-procedure. If the patient experienced a possible endpoint event and was treated at an outside facility, medical records will be obtained for review of whether the endpoint was met.

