#### F. Statistical Considerations:

**F1. Randomization and blinding:** Patients will be randomized (1:1:1) to one of the three ACT target groups (low, medium, or high) using a dynamic minimization algorithm so as to optimize the likelihood that balance between the low, medium, and high ACT target groups will be

achieved with respect to sex (male or female) and glomerular filtration rate (30 to 59 ml/min/1.73m^2 or ≥60 ml/min/1.73m^2). The algorithm will be implemented in RAVE RTSM, a secure web-based interface, and accessed by the study coordinator or other appointed study personnel. Randomization will be conducted after the diagnostic portion of the procedure on only patients who will require ACT monitoring. Since eligible patients will require ACT monitoring during PCI, we will not conduct the study in a strictly blinded fashion. However, study participants will not be informed of their randomization assignment.

**F2. Data collection and handling:** Electronic case report forms along with a corresponding secure REDCap database will be created for data collection (29). Data to be collected will include baseline demographics, comorbidities, procedural variables, in-hospital events, NACE component, and adverse events.

**F3: Definition of study outcomes:** Study endpoints are summarized in Appendix II.

**F3.1 Primary study endpoint:** Our **primary study endpoint is bleeding** and is defined as either a Bleeding Academic Research Consortium (BARC) hemorrhage grade of 1, 2, 3, or 5 or an EASY hematoma scale grade of I-V from the time of PCI to the time the patient is discharged from the hospital.

**F3.2 Primary safety endpoint:** Our **primary safety endpoint is a composite of net adverse clinical events (NACE) and stent thrombosis**, as defined by the Academic Research Consortium, from the time of PCI to the time the patient is discharged from the hospital.

**F3.2.1 NACE** is the composite of all-cause mortality, myocardial infarction (MI), stroke, target lesion revascularization, and major bleeding within 30 days after PCI.

**F3.2.2 MI** will be defined as any two of the following 3 criteria: 1) chest pain for at least 20 minutes; 2) elevation of cardiac biomarkers, preferably troponin, above the laboratory upper limit of normal; and 3) new pathological Q wave on electrocardiogram.

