## F5. Statistical analysis plans:

F5.1 Patient population for analysis: The primary analysis will include all randomized patients. Since patients will be randomized after the diagnostic portion of the procedure and the primary study outcome will be collected during their initial hospitalization after PCI, we anticipate negligible loss to follow-up and negligible imbalance between study arms. Analysis of the study aims will be conducted using an intent-to-treat approach, which means it will be an analysis including all randomized patients according to the group they were randomized regardless of whether or not the assigned ACT target was achieved.

F5.2 Primary analysis plan: Aim 1: The risk of in-hospital bleeding in the medium ACT target group and the high ACT target group will be compared to the risk of in-hospital bleeding in the low ACT target group using pair-wise chi-square tests (or Fisher's exact test). Relative risks and 95% confidence intervals will be reported. For these two tests of the primary study outcome, a two-sided p-value  $\leq 0.025$  will be considered statistically significant using the Bonferroni adjustment for multiple testing. This means that the overall two-sided level of significance for the trial will be 0.05. Aim 2: We will estimate the proportion of patients with each outcome (bleeding, NACE) along with 95% confidence intervals for the proportions using the Wilson score method separately for the three groups. Aim 3: We will create a 95% confidence interval for the difference in proportions of patients with NACE in the low and high ACT target groups using the Newcombe score method. This will be used to assess whether there is evidence of non-inferiority of low ACT target compared to high ACT target according to the definition in section F3.4.

F5.3 Secondary analysis plan: We will evaluate if associations between ACT target group (low, medium, high) and in-hospital bleeding are independent of sex, access site, and concomitant use of glycoprotein (GP) IIb/IIIa inhibitors (Aim 2) using a Cochran-Mantel-Haenszel test. For these pre-planned tests, a two-sided p-value  $\leq 0.0167$  will be considered statistically significant using a Bonferroni adjustment for multiple testing. Descriptive summaries and relative risks will be reported as in the primary analysis, except stratified by each of the patient or procedure characteristics.

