Baseline patient and procedure characteristics of the three groups will be reported as number and percentage for categorical variables and median and interquartile range for continuous variables. To evaluate the possibility of imbalance, we will make comparisons between the three randomized groups using a Kruskal-Wallis test for ordered or numeric variables and a chi-square test (or Fisher's exact test) for categorical variables. For those baseline characteristics with imbalance between groups, we will summarize the number and percentage as well as relative risk and 95% confidence intervals as was done with the pre-planned analyses of sex, access site, and concomitant use of glycoprotein (GP) IIb/IIIa inhibitors with stratification by the baseline characteristic. In addition, we will use a multivariable logistic regression model with in-hospital bleeding as our outcome measure and fixed effects for group (reference group = low ACT target), sex, access site, concomitant use of glycoprotein (GP) IIb/IIIa inhibitors, and any other baseline characteristics with evidence of potential imbalance between groups (p-value  $\leq 0.20$ ) allowing no more than one variable for every 10 patients who experience in-hospital bleeding.

F5.4 Exploratory analysis plan: We will explore the association of ACT target with individual components of bleeding and NACE using a Cochran-Armitage trend test and report the number and percent of patients with each component separately for each group. Adjustment for multiple testing will be conducted using the Holm step-down method.

F5.5 Interim analysis plan: A blinded review of the study's overall incidence of the primary study outcome and the primary safety endpoint will be planned after 50% of patients have completed the study. If this review suggests that assumed incidence used to plan the study is much higher than the actual event rate then we may reestimate the sample size to ensure the study is adequately powered. Since the analysis will be conducted blind to group assignment this will not introduce statistical bias and adjustment to the study's significance level is not required...

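### F5.3 stratifies by and adjusts for concomitant GP IIb/IIIa inhibitor use as if it were a baseline factor, but such use almost always starts after randomization and may depend on the assigned ACT target

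*Combined protocol and SAP*

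**What the plan says.** Three parts of the plan refer to GP IIb/IIIa inhibitors, and they do not use the same variable.

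- **Setting the range (D. Approach).** "ACT target ranges would be modified based on intended or provisional use of GP IIb/IIIa inhibitors".
- **The question (B.1.4, Aim 4).** The aim is the effect of "concomitant use of glycoprotein (GP) IIb/IIIa inhibitors on the association of ACT target with bleeding". The same paragraph promises a "pre-specified analysis with specific ACT targets in patients receiving GP IIb/IIIa inhibitors".
- **The analysis (F5.3).** The plan tests whether the association between target group and bleeding is "independent of sex, access site, and concomitant use of glycoprotein (GP) IIb/IIIa inhibitors (Aim 2) using a Cochran-Mantel-Haenszel test". The Aim 2 label there appears to be a slip, since the content is that of Aim 4. Relative risks are also reported by stratum. The logistic model has fixed effects for group, "sex, access site, concomitant use of glycoprotein (GP) IIb/IIIa inhibitors, and any other baseline characteristics with evidence of potential imbalance".

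Two design features fix the timing. The exclusion criteria in D list "Prior GP IIb/IIIa use within the previous 72 hours". F1 places randomization after the diagnostic part of the procedure and states that the trial is not strictly blinded, although participants are not told their arm.

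**The concern.** Of the three pre-planned factors in F5.3, sex is fixed before randomization and access site is normally settled by the end of the diagnostic portion. GP IIb/IIIa use is different: it is decided largely during the intervention, by an operator who can know the assigned target. F5.3 nevertheless lists it with baseline characteristics.

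A variable that the assignment can change should not be held fixed when estimating the effect of assignment. Suppose a lower target led to more thrombus, and so to more unplanned inhibitor use. Any bleeding caused by that extra use would be a consequence of the low target. Comparing arms within strata of use, or adjusting for use, removes that bleeding from the low arm, which favours the trial's hypothesis. If use and bleeding also share causes such as procedural complexity, the adjusted estimate is not a clean direct effect either.

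There is also a question of meaning. The range depends on intended or provisional use, while the strata depend on concomitant use. If these differ for some patients, the Aim 4 strata mix patients who were managed to different ranges.

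**Working it through.** **1. The plan's own figures.** The secondary threshold is 0.05/3 = 0.0167, as stated in F5.3. With 504/3 = 168 patients per arm and a two-sided 0.025 level, exact enumeration of the chi-square test gives 81.2% power for 5% vs 15% and 99.9% for 5% vs 25%. The statement of more than 80% power in F.4 is therefore reproduced. GP IIb/IIIa status does not enter that calculation.

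**2. Timing.** No use in the previous 72 hours (exclusion criterion), plus randomization after the diagnostic portion (F1), leaves almost no room for use to begin before assignment. The only gap is a dose given during the diagnostic portion itself.

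**3. Illustration with assumed rates.** The documents give no rate of GP IIb/IIIa use, no difference by arm, and no size for its effect on bleeding. Assume use of 8% (low) and 2% (high), and bleeding of 10% without and 30% with the drug in both arms.

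- Low: 0.92 × 0.10 + 0.08 × 0.30 = 0.116
- High: 0.98 × 0.10 + 0.02 × 0.30 = 0.104
- Overall RR = 0.116/0.104 = 1.12. Overall OR = (0.116/0.884)/(0.104/0.896) = 1.13
- Within each stratum the risks are equal, so RR = OR = 1.00

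At 168 per arm this is about 19.5 vs 17.5 patients with bleeding, a difference of 168 × 0.012 = 2.0.

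**4. A range of assumptions.** Let g be the proportion using the drug in an arm and r the bleeding risk ratio for use. With no direct effect of the target, the overall low/high RR is [1 + (r − 1)g_L] / [1 + (r − 1)g_H], while the within-stratum RR is 1.00. If instead the overall risks are the planned 5% and 25% (RR 0.20), the within-stratum RR is 0.20 divided by that same quantity. With g_H = 5%:

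| g_L | Overall RR, no direct effect (r = 1.5 / 2 / 3) | Within-stratum RR when overall RR is 0.20 (r = 1.5 / 2 / 3) |
|---|---|---|
| 5% | 1.000 / 1.000 / 1.000 | 0.200 / 0.200 / 0.200 |
| 10% | 1.024 / 1.048 / 1.091 | 0.195 / 0.191 / 0.183 |
| 15% | 1.049 / 1.095 / 1.182 | 0.191 / 0.183 / 0.169 |
| 20% | 1.073 / 1.143 / 1.273 | 0.186 / 0.175 / 0.157 |

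The first row shows the condition: when the arm does not change use, nothing is distorted.

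**5. Adding a shared cause.** This simulation had 1.5 million patients, no direct arm effect, and an OR of 2 for the drug on bleeding. A factor present in half the patients had an OR of 4 on use and an OR of 2 or 4 on bleeding. With use of 10–20% (low) vs 5% (high), the overall OR was 1.04–1.13 and the adjusted OR 0.93–0.99. Simulation noise is about 0.01: without the shared cause the adjusted OR should be 1.00, and it came out between 0.992 and 1.009. The reversal is therefore clear only towards the larger differences in use (for example 1.119 overall, 0.934 adjusted). With 5% use in both arms, both ORs stayed within 0.002 of 1.

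**6. Which variable is meant.** D uses intended or provisional use, B.1.4 uses both concomitant use and receipt, and F5.3 uses concomitant use. None of these sections defines the term, equates the variables, or provides for recording intent before randomization.

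**The case against.** The strongest reply is that this concerns secondary analyses only. Under F5.2, Aim 1 is an unadjusted comparison by randomized group with its own relative risks. The crude effect will be on the page whatever the adjusted model shows. Aims 2 and 3 do not use GP IIb/IIIa status. At the planned rates the distortion moves an RR of 0.20 only to between 0.157 and 0.195. The assumed mechanism is also uncertain: in Table 1, the two older, mainly balloon-angioplasty analyses link lower ACT to more abrupt closure or ischemic events, but the three later stent-era studies do not. All of this stands, and it limits the importance of the point. It does not make concomitant use a baseline variable.

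A reader might infer four stronger things that the documents do not support.

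- **That the plan says it analyses actual use.** It says concomitant use, undefined. Actual receipt is the likelier meaning, because B.1.4 speaks of patients receiving these agents, but that is an inference.
- **That patients are placed in the wrong target stratum.** The low, medium or high label is kept as randomized (F5.1) and stays correct. Whether the GP IIb/IIIa stratum departs from the range used depends on what provisional means. If it means use foreseen beforehand, some patients on the modified range never receive the drug. If it means as-needed use, which the title of one cited trial suggests by contrasting provisional with planned blockade, D may already modify the range for unplanned use. Figures 1 and 2 are not reproduced in the text reviewed, so this cannot be settled here.
- **That the adjusted comparison is biased outright.** It is biased only if the arm affects use.
- **That leaving intent out of the minimization is an error.** F1 seeks balance "achieved with respect to sex (male or female) and glomerular filtration rate". Not adding a further factor causes no bias.

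**Conclusion.** The point holds for the GP IIb/IIIa part of F5.3: the Cochran-Mantel-Haenszel analysis, the stratified relative risks and the adjusted logistic model. On the plan's own timing, concomitant use is in practice a post-randomization variable that the assigned target may affect, and F5.3 treats it as a baseline one. If use differs by arm because of the target, these analyses do not estimate the effect of assignment. Under the assumed rates, an overall RR of 1.02 to 1.27 (1.12 in the worked example) is moved to 1.00. With a shared cause of use and bleeding, the direction can reverse. With no arm effect on use, this bias is absent. Every rate behind these sizes is an assumption.

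Separately, B.1.4, D and F5.3 must be reconciled on which GP IIb/IIIa variable is meant. Aims 1 to 3, the sample size and the significance levels do not change.

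**What to change.** 1. Record intended or provisional GP IIb/IIIa use (yes/no) before randomization, with a definition of provisional. The documents do not say that the operator commits to this before assignment, so the form has to ask.
2. In F5.3, use that field in place of concomitant use, both as the Aim 4 stratum and as the logistic covariate. The minimum alternative for the model is to drop concomitant use from it.
3. Report actual use by arm descriptively. Label any analysis by actual use as exploratory and non-randomized.
4. Align the wording of B.1.4, D and F5.3, and correct the Aim 2 label in F5.3.

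The cost is one data field and some SAP wording, with no extra patients or procedures. The real downside is precision. If planned use were 0–5% (an assumption), a stratum of planned users would hold 0 to about 25 of 504 patients, at most about 8 per arm. It would be larger if provisional covers foreseen possible use. Aim 4 would then also be answered for patients in whom use was foreseen, with actual recipients only described. Adding the field to the minimization is optional.

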**Figure 1**

The ACT target algorithm closely mirrors practice guidelines for UFH supplementation and ACT monitoring (Figure 2)(4). The algorithm provides rigorous standardization to the process of ACT sampling and UFH supplementation to reduce the risk for bias in the study. Although there will be multiple ACT values for each PCI procedure, the use of the ACT value prior to device activation will be the “target” for the purposes of the trial. In the event that an ACT prior to device activation was not obtained, the ACT value closest to the time of initial device activation will be used and the procedure time between the ACT sample and device activation will be recorded.

**Figure 2**

The Hemochron Signature Elite (Hemochron® Jr.) whole blood microcoagulation system (International Technidyne Corporation, Edison, NJ) for ACT is the POC test performed in the cardiac catheterization laboratory at Mayo Clinic Florida. The ACT demonstrates linear correlation to the anticoagulation effects of heparin to 2.5 units/L of blood. The device is intended for clinical use during *in vitro* diagnostic testing of whole blood for POC monitoring of anticoagulation intensity in UFH-treated patients undergoing medical procedures. The test result is automatically converted to a reference Celite® ACT value and both displayed and electronically recorded on the device. No other ACT assay system will be used for the OPTIMAL-ACT trial. Although some patients receive non-UFH anticoagulants, ACT is most commonly used to monitor patients receiving UFH and undergoing cardiac catheterization. The Mayo Clinic Department of Laboratory Medicine and Pathology oversees POC testing in the cardiac catheterization laboratories at Mayo Clinic Florida. For the OPTIMAL-ACT trial, collaborators from the Mayo Clinic Department of Laboratory Medicine and Pathology will be co-investigators to provide technical expertise regarding POC testing using ACT. Quality controls are outlined in an institutional Standard Operating Procedure document.

**E. Preliminary Work:** Data for the relationship between ACT and outcomes are sparse in contemporary PCI practice and guideline recommended targets for ACT during PCI were based on small studies in angioplasty alone settings (23) or proof-of-concept studies that did not report clinical outcomes (24). Table 1 summarizes the existing literature comprising the largest studies with regard to ACT target values and outcomes. These studies have primarily been derived from “lower-risk” populations in trials and are entirely post-hoc analyses, the exception being the registry based design of the Mayo Clinic experience by Rajpurohit et al ([name],

senior author), representing the largest study on this topic to date (18). However, the study is primarily limited in terms of drawing firm conclusions by its retrospective design.

